3.1.15 ECOG PS 0-1

3.1.16 Patient must sign a study-specific consent form prior to registration

3.1.17 Ability to understand and the willingness to sign a written informed consent. A signed informed consent must be obtained prior to any study specific procedures.

3.2 Exclusion Criteria

3.2.1 Patients with known brain metastases. Patients with neurological symptoms must undergo a CT scan/MRI of the brain to exclude brain metastases.

3.2.2 Uncontrolled intercurrent illness including, but not limited to, ongoing or active serious infection $>$ CTCAE Grade 2, symptomatic congestive heart failure, unstable angina pectoris, cardiac ventricular arrhythmia requiring anti-arrhythmic therapy, or psychiatric illness/social situations that would limit compliance with study requirements. Patients must not have unstable angina (angina symptoms at rest) or new onset angina (began within the last 3 months) or myocardial infarction within the past 6 months.

3.2.3 Uncontrolled hypertension defined as systolic blood pressure $>$ 150 mmHg or diastolic pressure $>$ 90 mmHg, despite optimal medical management.

3.2.4 Known human immunodeficiency virus (HIV) infection or chronic Hepatitis B or C.

3.2.5 Thrombotic or embolic events such as a cerebrovascular accident including transient ischemic attacks within the past 6 months.

3.2.6 Pulmonary hemorrhage/bleeding event \geq CTCAE Grade 2 within 4 weeks of first dose of study drug.

3.2.7 Any other hemorrhage/bleeding event \geq CTCAE Grade 3 within 4 weeks of first dose of study drug.

3.2.8 Serious non-healing wound, ulcer, or bone fracture.

3.2.9 Evidence or history of bleeding diathesis or coagulopathy.

3.2.10 Major surgery or significant traumatic injury within 4 weeks of first study drug.

3.2.11 Use of strong CYP3A4 inducers (See Section 4.6).

- 3.2.12 Known or suspected allergy to sorafenib or any agent given in the course of this trial.**
- 3.2.13 Any condition that impairs patient's ability to swallow whole pills.**
- 3.2.14 Any malabsorption problem.**
- 3.2.15 Pregnant or lactating women are excluded from this study because of possible risk to the fetus or infant.**
- 3.2.16 Patients with a "currently active" second malignancy other than non-melanoma skin cancers are not to be registered. Patients are not considered to have a "currently active" malignancy if they have completed therapy and considered by their physician to be at less than 30% risk of relapse.**
- 3.2.17 Any uncontrolled thyroid disease.**
- 3.2.18 Requirement for hemodialysis or peritoneal dialysis**

3.3 Removal of Subjects from Study

3.3.1 Criteria for stopping therapy:

- Substantial non-compliance with the requirements of the study.
- Any adverse event which, in the Investigator's opinion, requires termination of the study medication.
- Disease progression, unless at the discretion of the investigator (in collaboration with Bayer/Onyx) continued treatment with study drug is appropriate.
- The patient would benefit from additional radiation therapy beyond that specified in the protocol.
- Request by the patient or a legal representative/relative to stop the treatment.
- The patient presents with a beta-HCG test consistent with pregnancy. Pregnancy will be reported along the same timelines as a serious adverse event
- The patient uses illicit drugs or other substances that may, in the opinion of the Investigator, have a reasonable chance of contributing to toxicity or otherwise interfering with results.
- The development of a second malignancy that requires treatment, which would interfere with this study.
- The patient is lost to follow-up.
- Interruption in study drug's administration for greater than 3-week delay. Following surgery, interruption in study drug's administration is allowed for up to 10-weeks from initial surgery.
- Development of an intercurrent illness or situation which would, in the judgment of the investigator, affect assessments of clinical status and study endpoints to a significant degree.

3.3.2 Criteria for study withdrawal:

- Disease progression, unless at the discretion of the investigator (in collaboration with Bayer/Onyx) continued treatment with study drug is

appropriate.

- Study closure,
- Unacceptable adverse event(s),
- Patient decision to withdraw from the study, or
- In the judgment of the investigator, further treatment would not be in the best interest of the patient.

The Investigator will make every reasonable effort to keep each patient in the study unless it is in the patient's best interest to discontinue participation. If a patient is removed from the study or declines further participation, all End of Treatment evaluations should be performed if the patient is willing and able to be assessed. A description of the reason(s) for withdrawal from the study will be recorded on the case report form (CRF). The Investigator should also ensure that all patients are followed up for survival and recurrence after the Final Visit.

Relevant visit data should be entered on the CRF and any unused study medication will be accounted for and returned for all patients participating in the study, even for a brief period of time. Patients who discontinue following entry will have relevant information completed and recorded on the CRF. All patients who discontinue because of adverse events or clinically significant laboratory abnormalities should be followed up until they recover or stabilize, and the subsequent outcome will be recorded. If any patient should die during the trial or within 30 days of stopping study treatment, the Investigator will inform the OHSU IRB and the Bayer representative. The cause of death should be recorded in detail, within 24 hours, on a serious adverse event (SAE) form and reported to the sponsor Drug Safety Unit (refer to Section 10)).

4. TREATMENT PLAN

TX	SORAFENIB RUN-IN	CYCLE 1 DAYS	CYCLE 2 DAYS	CYCLE 3 DAYS	SURGERY	CYCLE 4 DAYS	CYCLE 5 DAYS	CYCLE 6 DAYS
EPI		15-17	OMIT	57-59		99-101	120-122	141-143
IFOS		15-17	36-38*	57-59		99-101	120-122	141-143
MESNA		15-17	36-38*	57-59		99-101	120-122	141-143
SORAFENIB	1-14	15-35	36-56	57-71**	85-98**	99-119	120-140	141-155
PEG-FILGRASTIM◆		18	39	60		102	123	144
RT			36-45*			BOOST***		
SURGERY					78**			

1 cycle = 21 days in length

- ◆ PEG-Filgrastim should be administered 24-48 hours after completing chemotherapy. 10 days of filgrastim may be substituted.
- * Radiation administration will consist of 8 fractions over 10 days, as it is common practice in many centers not to administer radiation therapy on weekends. Whenever possible, both radiation and chemotherapy should be administered together on days 36-38. Initiating chemoradiation on a Monday, Tuesday, or Wednesday for cycle 2 will help ensure concomitant administration during these 3 days prior to the weekend break.
- ** Sorafenib should be discontinued 1 week before surgery and resumed 1 week after surgery. Note that the timing of surgery and resumption of post-operative chemotherapy presented here are estimations. While adherence to this schedule is a goal, treatment-related complications and other logistical factors may alter scheduled events. In general, surgery should be planned for 2-4 weeks after the initiation of chemotherapy for cycle 3. Deviation from this schedule will be reported in the final analysis. In case of delays, the dates specified above should be appropriately recalculated. If a major wound complication requires additional surgery, reinstitution of chemotherapy (cycle 4) should be initiated only after adequate wound healing has been achieved (a minimum of 2 weeks following the second surgery). Patients who require a delay of greater than 10 weeks since initial surgery due to inadequate wound healing will be removed from further protocol therapy.
- *** For patients with positive surgical margins, 12 Gy (200 cGy x 6 fractions) will be given by external beam prior to restarting chemotherapy. Begin radiation 2 weeks after surgery (approximately day 91) assuming wound is healing well.

4.1 Study Drug

Sorafenib will be administered orally 400 mg once daily. Sorafenib will begin 2 weeks before first chemotherapy cycle with epirubicin and ifosfamide. Sorafenib will be held 1 week before and after surgery

4.2 Chemotherapy Dose and Suggested Administration Guidelines (may be modified per institutional standards)

Chemotherapy can be administered on either an inpatient or outpatient basis. No investigational or commercial agents or therapies other than those described in the protocol may be administered with the intent to treat the patient's malignancy. Patients will receive 3 cycles of pre-operative chemotherapy and 3 cycles of post-operative chemotherapy.

Recommended hydration is 0.45 NS + 50 mEq NaHCO₃ 1L over 2 hours prior to ifosfamide daily.

- Epirubicin: 30 mg/m²/day I.V., days 1-3 of each cycle. Epirubicin is to be omitted during cycle 2 (concomitant chemoradiation)
- Ifosfamide: 2.5 g/m² over 90 minutes I.V., days 1-3 of each cycle. Begin after 1 L hydration

- Mesna: Suggested dosing: 850 mg/m² mixed in same bag as ifosfamide, then 850 mg/m² I.V. over 15 minutes given 4 hours and 8 hours after start of ifosfamide, days 1-3 of each cycle
- PEG-filgrastim 6 mg administered as a subcutaneous injection starting 24-48 hours after completion of chemotherapy (may substitute filgrastim 5 mcg/kg/day (rounded to nearest vial size) administered as a subcutaneous injection starting 24-48 hours after completion of chemotherapy for 10 days, or until white blood count has recovered after nadir (ANC > 10,000)

4.3 Radiation

Treatment is to consist of one course of external beam radiation therapy (EBRT) coinciding with the start of cycle 2 of chemotherapy. Treatment will consist of a total dose of 28 Gy (350cGy x 8 fractions in 10 days). If treatment falls on a weekend or holiday, treatment can resume the next business day.

The target volume of radiation therapy will include the site of the primary lesion and those tissues suspected of involvement by microscopic disease to a clinically important probability. Physical exam in conjunction with MRI or CT scans obtained during evaluation will be used in defining the target volume. The margins beyond clinically or radiologically-evident sarcoma will be 7 cm. Optimal field arrangement, beam parameters, and shaped blocks will be used to achieve the closest approximation of treatment volume to target volume to minimize irradiation of uninvolved normal tissue. Immobilization devices should be used daily to ensure reproducibility of treatment.

Post-operative EBRT boost will be given for patients with positive margins. The radiation treatment is to be completed by administering 12 Gy in 6 fractions (once a day) to the bed of the residual tumor (including a margin of 1 cm). Boost will not be given for patients with 100% necrosis. EBRT will begin approximately 2 weeks following resection, assuming there is satisfactory healing of the surgical wound. The target volume for the post-operative radiation therapy will be the tumor bed as defined by the operative and pathological findings. Chemotherapy can resume thereafter.

4.4 Surgery

Surgical treatment necessary to resect the tumor with negative margins should be used. All lesions of the trunk and extremities will be treated with conservative resection (minimal wide excision) after pre-operative therapy. Surgical resection should remove as wide a margin of tissue around the tumor as possible without compromising function. Dissection should always be done through grossly normal tissue planes and should be done beyond fascial plane adjacent to the tumor. If the tumor is close to or displaces major vessels or nerves, these need not be removed if the adventitia or perineurium is removed and the margin is not involved pathologically. Frozen section at the time of surgery should be done from the closest margin and should be confirmed as being free of tumor. If postoperative pathology evaluation reveals positive soft-tissue margins other than bone, nerve, or large blood vessels, this margin should be resected if possible. If bone, major blood vessel or nerve is microscopically positive additional radiation should be given as

noted in the protocol. In general, lymph node dissection is not recommended, but a sampling can be performed if the primary tumor is over a major node station. Primary tumors overlying major lymph node stations may best be treated with surgical resection including node dissection. Marker clips (titanium) may be placed to help guide the radiation oncologist. Closed wound suction drainage should be used in all anatomic regions (Davol, Hemovac, etc.) The drains should exit the skin close to the edge of the surgical incision. External compression for extremity resections with ace wraps or compression dressings is advised.

State clearly in the operative note what type of surgical procedure was performed, and from where the frozen section of the margins was taken.

Because all patients will have had radiation, special care must be given to skin flaps. Use of muscle flaps, pedicled myocutaneous flaps, and even free flaps is encouraged to fill dead space and used if there is any concern about the viability of the wound flaps.

In general, the following principles should be followed in post-operative management of these patients:

- Maintain staples or skin sutures per surgeon preference but because of potential delay in wound healing, 3-4 weeks is recommended
- Leave drains until the drainage meets the criteria for surgeon preference for discontinuation
- Begin rehabilitation slowly

Resectability will depend upon the judgment of the operating surgeon. For the extremities, resection must be limb salvage procedure. For other anatomic areas, it must be the judgment of the operating surgeon that he/she may reasonably expect to obtain negative margins. Extremity patients who are not resectable without amputation may be amputated, and should complete chemotherapy per protocol. Unresectable tumors elsewhere may be palliated with additional chemotherapy, per protocol. Patients who would benefit from additional radiation therapy will be withdrawn from protocol therapy.

Note that documentation of wound complications is an integral part of this clinical trial. Wound complications are defined in section 8.5 and must be accurately recorded and reported to the coordinating center.

4.5 Supportive Care Guidelines

Appropriate anti-emetics per institutional standard and at the investigator's discretion should be used with this highly-emetogenic regimen.

Use of erythroid growth factors to support hemoglobin levels are permitted, at the discretion of the investigator.

Prophylactic antibiotics for prevention of neutropenic fever may be used at the discretion of the investigator. Use of prophylactic antibiotics must be recorded in the case report forms.

4.6 Other Concomitant Medications

Sorafenib is metabolized primarily by liver enzymes, in particular CYP3A4. Caution is recommended when administering sorafenib with inducers of the CYP3A4 family.

Concurrent administration of strong CYP3A4 inducers (such as, phenytoin, rifabutin, and rifampin) is not permitted. In a clinical interaction study, concurrent administration of sorafenib with rifampin resulted in a 37% decrease in mean sorafenib AUC. Other agents known to moderately induce CYP3A4 should be avoided if possible.

4.7 Duration of Therapy

Treatment should continue until the end of protocol therapy or until one of the following criteria applies:

Disease progression,

The patient would benefit from additional radiation therapy beyond that specified in the protocol,

Intercurrent illness that prevents further administration of treatment,

Unacceptable adverse events(s),

Greater than 3-week delay in therapy due to adverse event

The patient presents with a beta-HCG test consistent with pregnancy.

Patient or legal representative/relative requests to withdraw from the study, or

General or specific changes in the patient's condition render the patient unacceptable for further treatment in the judgment of the investigator.

5. DOSE MODIFICATIONS

5.1 Sorafenib Dose Modifications

General Considerations. Sorafenib dosing will be modified for adverse events that are at least in-part *attributable* to sorafenib according to the following dose levels:

Dose Level	Sorafenib
0	400 mg once daily
-1	200 mg once daily
-2*	200 mg every other day

All patients will start treatment at dose level 0.

Patients will be removed from protocol treatment if dose reduction below -2 is indicated.

5.1.1 Dose Modifications for Sorafenib for Hand-Foot Skin Reaction

Grade	Occurrence	Suggested Dose Modification
Grade 1 Minimal skin changes or dermatitis (e.g., erythema, edema, or hyperkeratosis) without pain	Any	Promptly institute supportive measures such as topical therapy for symptomatic relief and continue sorafenib treatment
Grade 2 Skin changes (e.g., peeling, blisters, bleeding, edema, or hyperkeratosis) with pain; limiting instrumental ADL	First	
Promptly institute supportive measures such as topical therapy for symptomatic relief and consider a decrease of sorafenib by one dose level for a minimum of 7 days and up to 28 days
 
 • If toxicity resolves to grade 0–1 after dose reduction, increase sorafenib back to previous dose level • If toxicity does not resolve to grade 0–1 despite dose reduction, interrupt sorafenib treatment for a minimum of 7 days and until toxicity has resolved to grade 0–1. 
 ▪ When resuming treatment after dose interruption, resume sorafenib at a one dose level reduction ▪ If toxicity is maintained at grade 0–1 at reduced dose for a minimum of 7 days and up to 28 days, increase back sorafenib to previous dose level
	Second or Third occurrence	
As for first occurrence. Upon resuming sorafenib, decrease dose by one dose level.
 
Decision whether to dose re-escalate should be based on clinical judgment and patient preference.

	Fourth occurrence	
Decision whether to discontinue sorafenib should be made based on clinical judgment and patient preference

Grade 3 Severe skin changes (e.g., peeling, blisters, bleeding, edema, or hyperkeratosis) with pain; limiting self care ADL	First occurrence	
Institute supportive measures such as topical therapy for symptomatic relief and interrupt sorafenib treatment for a minimum of 7 days and until toxicity has resolved to grade 0–1
 
 • When resuming treatment after dose interruption, decrease sorafenib by one dose level • If toxicity is maintained at grade 0–1 at reduced dose for a minimum of 7 days and up to 28 days, increase by one dose level
	Second occurrence	
As for first occurrence. Upon resuming sorafenib treatment, decrease dose by one dose level.
 
Decision whether to dose re-escalate should be made based on clinical judgment and patient preference.

	Third occurrence	
Decision whether to discontinue sorafenib treatment should be made based on clinical judgement and patient preference.

5.1.2 Dose Modifications for Sorafenib-Associated Hypertension

Hypertension is a known and potentially serious adverse event associated with sorafenib treatment. Patients will have their blood pressure monitored and recorded weekly during the first 6 weeks of therapy, either at the doctor's office or by using any calibrated electronic device (such as those found at a local drug store or pharmacy). Patients will record their weekly blood pressure during the first 6 weeks on their drug diary, a copy of which will remain in the research chart. If the patient's blood pressure is elevated at any time (>150/100), even outside clinic visits, they should contact their treating physician.

Grade (CTCAE v4.0)	Antihypertensive Therapy	Blood Pressure Monitoring	Sorafenib Dose
Grade 1	None	Routine	No change
Grade 2	Initiate monotherapy (suggest dihydropyridine calcium-channel blocker)	Increase frequency and monitor (by health professional) every 2 days until stabilized	No change
Grade 3	Add agent(s): Ca ⁺⁺ channel blocker (if not already used), K ⁺ channel opener (angiotensin blockers), beta-blocker, thiazide diuretic	Increase frequency and monitor (by health professional) every 2 days until stabilized; continue qod monitoring to stabilization after dosing restarted.	Hold* sorafenib until symptoms resolve and diastolic BP < 100 mm/Hg. Resume treatment at 1 dose level lower
Grade 4			Off protocol therapy

* Patients requiring a delay of > 21 days should go off protocol therapy

CTCAE v4.0 definitions

Grade 1: Prehypertension (systolic BP 120 - 139 mm Hg or diastolic BP 80 - 89 mm Hg)

Grade 2: Stage 1 hypertension (systolic BP 140 - 159 mm Hg or diastolic BP 90 - 99 mm Hg); medical intervention indicated; recurrent or persistent (≥24 hrs); symptomatic increase by >20 mm Hg (diastolic) or to >140/90 mm Hg if previously WNL; monotherapy indicated. Pediatric: recurrent or persistent (≥24 hrs) BP >ULN; monotherapy indicated

Grade 3: Stage 2 hypertension (systolic BP ≥160 mm Hg or diastolic BP ≥100 mm Hg); medical intervention indicated; more than one drug or more intensive therapy than previously used indicated. Pediatric: Same as adult

Grade 4: Life-threatening consequences (e.g., malignant hypertension, transient or permanent neurologic deficit, hypertensive crisis); urgent intervention indicated. Pediatric: Same as adult

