8.7 Schedule of Events

	Prior to Registration	Prior to Day 1 of each cycle*	Time of Pre-Surgical Restaging**	Post Treatment Follow-up
Tests & Observations				
History and Progress Notes	X	X	X	X
Physical Examination	X	X	X	X
Pulse, Blood Pressure###	X	X	X	X
Height/Weight***	X	X		
Performance Status	X	X	X	X
Treatment Toxicity Assessment		F	F	F
Pathology Review	A		A	
Laboratory Studies				
CBC, Differential, Platelets	X	B,C	X	PRN
Serum Chemistries#	X	B,C	X	PRN
Urinalysis	X	C		
Pregnancy Test##	X	X		
INR	X	H		
EKG	X			PRN
MUGA or ECHO	X		X	D
Blood for correlative studies (Section 7.1)	X	X	X	
Staging				
Chest CT	X		X	E
MRI or CT of primary site	G		G	E

* To be performed within 1 week of each chemotherapy cycle

** After completion of cycle 3 of chemoradiotherapy and within 4 weeks of surgery

*** Height only needs to be checked prior to cycle #1 if the patient's height is stable (i.e. not currently in puberty).

Electrolytes (including Phos, Mg), BUN, creatinine, bilirubin, AST, ALT, alkaline phosphatase

For women of childbearing potential. Screening pregnancy test does not need to be repeated if within 7 days of start of Sorafenib run-in. Will be repeated prior to each cycle of chemotherapy.

Blood pressure to be monitored weekly during the first 6 weeks of protocol treatment

A Initial diagnostic pathology specimen as well as post-operative specimen must be submitted for central review. Both specimens may be submitted together after surgery

B To be checked once weekly during each cycle or as clinically indicated

C Must be checked within 24 hours prior to each chemotherapy cycle

D As clinically indicated

E Post-treatment imaging studies for disease recurrence is at investigator's discretion. It is suggested that a chest CT or chest X-ray be performed every 4 months for the first 2 years, every 6 months for the 3rd year, and yearly for the 4th and 5th year. It is suggested that MRI or CT of the primary site be obtained yearly for the first 3 years.

F Toxicity assessments per CTCAE v 4.0 (See section 8.3). Long term follow-up for radiation toxicity and limb function required per section 8.3

G An MRI or CT of the primary tumor should be performed within 6 weeks prior to registration and again prior to surgery per standard care decision of the subject's surgeon

H INR should be closely monitored for patients receiving warfarin. INR does not need to be monitored during study for patients not receiving warfarin.

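### The blood pressure at which patients are told to call (>150/100) does not match the grade 2 and grade 3 limits of the action table in Section 5.1.2

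*Combined protocol and SAP*

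**What the plan says.** Section 5.1.2 has blood pressure checked weekly for the first 6 weeks, either in the office or on a calibrated device elsewhere, such as one in a drug store. The patient writes the reading in the drug diary. The instruction for acting between visits is that if the patient's "blood pressure is elevated at any time (>150/100), even outside clinic visits, they should contact their treating physician".

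The definitions printed under the action table in that section are:

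- "Grade 2: Stage 1 hypertension (systolic BP 140 - 159 mm Hg or diastolic BP 90 - 99 mm Hg); medical intervention indicated"
- "Grade 3: Stage 2 hypertension (systolic BP ≥160 mm Hg or diastolic BP ≥100 mm Hg"

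For grade 2 the table asks for drug treatment, "Initiate monotherapy (suggest dihydropyridine calcium-channel blocker", and closer checks, "Increase frequency and monitor (by health professional) every 2 days until stabilized", with no change to sorafenib. For grade 3 it adds "Hold* sorafenib until symptoms resolve" and requires diastolic pressure to be below 100 before restarting.

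Section 8.7 lists blood pressure before each cycle, "To be performed within 1 week of each chemotherapy cycle", and repeats the weekly check for the first 6 weeks. No other text gives patients a lower value at which to call.

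**The concern.** The section sets out steps that begin at one level and tells patients to report at another. A patient who follows the call sentence exactly can hold a reading for which the table has an action, while nobody able to take that action knows of it. In the grade 2 range the steps at risk of delay are monotherapy and the 2-day checks. At a diastolic of exactly 100 it is the sorafenib hold.

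The slash form adds a second problem. The grades are written with an explicit *or*, but the call line has neither *or* nor *and*, so two patients with the same reading could reasonably act differently. The section itself describes hypertension on sorafenib as potentially serious, so its one patient-facing trigger should be unambiguous.

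**Working it through.** The plan gives no figure to reproduce here. The check compares thresholds and then looks at the schedule. S is systolic and D diastolic, in whole mm Hg.

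**Inputs**
- Call line: >150/100 (5.1.2).
- Grade 2 range: S 140–159 or D 90–99. Grade 3 range: S ≥160 or D ≥100 (5.1.2).
- Sorafenib run-in on days 1–14, cycle 1 from day 15, cycles of 21 days (Section 4).
- Clinic blood pressure before each cycle (8.7).

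**Step 1: either value is enough (the more natural reading).** A call needs S >150 or D >100, so there is no call when S ≤150 and D ≤100.
- Grade 2 range without a call: S 140–150 with D ≤99, or D 90–99 with S ≤150. Within grade 2, only S 151–159 prompts a call.
- Grade 3 range without a call: S ≤150 rules out the systolic criterion, so D must be both ≥100 and ≤100. The gap is D = 100 with S ≤150, caused by > in the call line against ≥ in the grade.

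**Step 2: both values are needed.** A call needs S >150 and D >100.
- A reading in the grade 2 range has D ≤99, so none prompts a call.
- A grade 3 reading prompts a call only if S ≥151 and D ≥101.

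**Step 3: examples**

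| Reading | Range | Call, either value | Call, both values |
|---|---|---|---|
| 148/98 | grade 2 | no | no |
| 150/99 | grade 2 | no | no |
| 151/99 | grade 2 | yes | no |
| 145/100 | grade 3 | no | no |
| 145/105 | grade 3 | yes | no |
| 175/95 | grade 3 | yes | no |
| 151/101 | grade 3 | yes | yes |

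**Step 4: size as a count of values.** Take all pairs with S 120–159 and D 80–99. Those in the grade 2 range number 40 × 20 − 20 × 10 = 600. On the either-value reading, those that prompt a call have S 151–159: 9 × 20 = 180. The remainder is 420/600 = 70%. On the both-values reading it is 100%. This weights every pair equally, which is an assumption. The documents give no distribution of readings, so 70% is not a share of patients.

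**Step 5: the wait.** A reading taken in the office involves no wait. A home reading in the gap waits for the next contact at which staff take a blood pressure or look at the diary. If only the pre-cycle check counts:
- run-in: day 1 to day 15 at the latest, up to 14 days;
- later: 21 days between successive pre-cycle checks made at the same point in the cycle.

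That gives about 2 to 3 weeks if nothing else intervenes. Chemotherapy visits, with toxicity assessed at each visit (8.3), may shorten it, but no text says when the diary is reviewed.

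**Step 6: the replacement line.** S ≥140 or D ≥90 is exactly the grade 2 and grade 3 ranges combined. It covers every reading in them and none below.

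**The case against.** The best defence is that the two thresholds do different jobs. The call line is an alarm for patients and the table is a guide for clinicians, whose duties hold whatever the patient was told. An alarm set above the level for routine treatment is a legitimate choice. That stands as a possibility, though the text does not state it as the intention. It also explains neither the missing *or*/*and* nor a call line that leaves out a diastolic of 100, the value at which the table holds the drug.

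The systolic part agrees with the exclusion criterion in 3.2.3 (above 150 despite optimal management). The diastolic part does not: 3.2.3 uses 90, which is 10 mm Hg lower.

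Several further points stand and limit the concern:
- Readings in the gap are written in the diary and kept, so they are not lost. Being recorded is not the same as being seen in time.
- The grade 2 definition also refers to recurrence, persistence for at least 24 hours, or a symptomatic rise. One home reading of 148/98 may therefore not yet require any step.
- The drug diary is not among the documents, so what patients are actually told cannot be confirmed.

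A reader might infer more than the documents support, in three ways:
- *The wait is at most a week, because patients are checked weekly from cycle 1.* The relevant footnote in 8.7, "To be checked once weekly during each cycle or as clinically indicated", is attached to blood counts and serum chemistries. It is not attached to the blood pressure row, and nothing links a blood draw to diary review. Neither a one-week limit nor a description of the delay as brief is established.
- *Most patients with grade 2 hypertension are missed.* Only threshold values can be counted, not patients.
- *Grade 3 readings generally go unreported.* On the more natural reading the grade 3 gap is the single diastolic value of 100. The wide gap needs the both-values reading.

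**Conclusion.** The mismatch is real and visible within one section, and it is minor. The threshold comparison is certain on either reading of the call line. The consequence is less certain: a possible delay to grade 2 measures that leave the sorafenib dose alone, and in a narrow case (or a wider one, if both values are required) a delay to the sorafenib hold. The length of the delay is not bounded by the documents. The figure of about 2 to 3 weeks assumes a home reading that staff first learn of at the next pre-cycle check. How many patients would have such readings is unknown. The primary endpoint, the sample size and the analysis are unaffected.

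**What to change.** Replace the call sentence in 5.1.2 with one tied to the grades and with an explicit *or*. Patients contact the study team the same day for systolic ≥160 or diastolic ≥100, and also for systolic ≥140 or diastolic ≥90 when a repeat reading confirms it. The repeat reading respects the recurrence and persistence wording and limits unnecessary calls. The same-day line closes the gap at a diastolic of 100. If the drug diary repeats the old line, it should change too.

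The cost is one sentence and some extra calls, including calls from patients who were eligible with systolic pressure of 140–150 at entry.

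### The grade 3 hypertension restart rule has no systolic condition, so sorafenib may restart while systolic pressure is still in the grade 3 range

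*Combined protocol and SAP*

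**What the plan says.** The grade 3 row of the table in Section 5.1.2 has three parts.

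- **Treatment:** antihypertensive agents are added.
- **Monitoring:** a health professional checks blood pressure every 2 days until it is stable, with the further instruction to "continue qod monitoring to stabilization after dosing restarted".
- **Sorafenib:** the drug is held until symptoms have resolved and "diastolic BP < 100 mm/Hg. Resume treatment at 1 dose level lower". A footnote adds: "Patients requiring a delay of > 21 days should go off protocol therapy".

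The grade definition printed under the table reads "Grade 3: Stage 2 hypertension (systolic BP ≥160 mm Hg or diastolic BP ≥100 mm Hg", followed by clauses on the need for medical intervention and for more than one drug or more intensive therapy.

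Two other places give numeric pressure limits. Section 3.2 excludes patients at entry with "Uncontrolled hypertension defined as systolic blood pressure" above 150 mm Hg, or diastolic above 90, despite optimal management. Section 5.1.2 tells patients to contact their physician if "blood pressure is elevated at any time (>150/100), even outside clinic visits".

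**The concern.** The rule that starts the hold has a systolic limb and the rule that ends it does not. A patient held only because of systolic pressure is released on a measurement that was never abnormal enough to cause the hold.

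The omission is out of keeping with the rest of the protocol. The other three sets of numeric pressure limits (entry, patient contact, grade definitions) all include systolic pressure. Elsewhere in Section 5.1, the rules that hold sorafenib and name a release grade set it below the grade that triggered the hold. Grade 3 hand-foot reaction must fall to grade 0–1, other grade 3 non-hematologic toxicity to grade 1 or less, and grade 3 hematologic toxicity to grade 2 or less.

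What is at stake is patient safety. Section 5.1.2 itself treats hypertension as a recognised and possibly serious effect of sorafenib. Section 6.1 lists hypertensive crisis and myocardial ischemia or infarction among its uncommon events, and Section 6.2 describes the cardiotoxicity of epirubicin, which is given in the same regimen.

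**Working it through.** The plan gives no figure to reproduce here. The check compares the trigger with the release rule, reading by reading.

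**Inputs (all from Section 5.1.2)**
- Blood pressure limb of grade 3: S ≥ 160 or D ≥ 100.
- Written release rule: no symptoms and D < 100.
- Release rule with a systolic condition added: no symptoms, D < 100 and S < 160.

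The printed grade 3 definition also has a therapy clause. To avoid depending on how that clause combines with the pressure limb, take patients who are asymptomatic and for whom added drug treatment is indicated. Those with S ≥ 160 or D ≥ 100 are then grade 3 on any reading.

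| Reading (S/D) | Grade 3 pressure | Released as written | Released with S < 160 added |
|---|---|---|---|
| 160/99 | yes | yes | no |
| 170/90 | yes | yes | no |
| 175/92 | yes | yes | no |
| 180/85 | yes | yes | no |
| 150/100 | yes | no | no |
| 159/99 | no | yes | yes |

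Every reading with S ≥ 160 and D < 100 is both grade 3 and releasable, so the minimum hold is 0 days. With the systolic condition added, no reading in the grade 3 pressure range is releasable. A patient controlled to 130/80 on two drugs can restart under either version.

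**Size in the 175/92 example**
- Above the grade 3 lower bound: 175 − 160 = 15 mm Hg.
- Above the entry limit: 175 − 150 = 25 mm Hg.
- Restart dose, one level down from 400 mg daily: 200 mg daily, a 50% reduction. The next level is 200 mg every other day, which averages 100 mg per day (a 75% reduction). Below that, Section 5.1 states: "Patients will be removed from protocol treatment if dose reduction below -2 is indicated".

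**Does other text close the gap?**
- Section 5.1.3 requires recovery to grade 1 or less after a grade 3 non-hematologic event, but its title limits it to other sorafenib toxicities. Hypertension has its own table.
- The systolic limit of 150 in Section 3.2 applies at enrolment only.
- The 150/100 figure in Section 5.1.2 tells the patient when to call. It is not a restart condition.
- The word on stabilization in the grade 3 row governs how often pressure is checked. Because the same cell continues monitoring to stabilization after dosing resumes, it does not make stability a condition of restart.

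**The case against.** The strongest reply is that the 0-day hold comes from reading one cell alone. The row as a whole adds drugs, checks pressure every 2 days until stable, holds sorafenib and then continues checking. An instruction to hold until something happens presupposes a real hold, and few clinicians would restart at a systolic pressure of 175. This stands as a forecast of conduct. It does not supply the missing criterion, and stability is nowhere stated as a condition of restart.

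A second reply is that a patient restarted at 160 or above is still grade 3 and would be held again. The cell does not say so. If it worked that way, the same release rule would again be met at once. The dose would step down to removal without systolic recovery ever being required.

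Third, the protocol never compels a restart. Section 3.3 lets the investigator end treatment for any adverse event that in the investigator's opinion "requires termination of the study medication", and Section 4.7 has similar provisions. This is correct and limits the harm.

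Fourth, the entry limit of 150/90 is not the on-treatment standard, since grade 2 pressures need no change of sorafenib. That is fair. The 15 mm Hg excess over the grade 3 bound is the relevant comparison, the 25 mm Hg figure is only context, and both depend on an illustrative reading.

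Last, one part of the printed grade 2 definition uses a diastolic rise alone. The contrast with the other limits therefore holds for each set as a whole, not for every clause.

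**Conclusion.** The concern holds, as a minor point. Followed as written, the grade 3 row allows an asymptomatic patient with systolic pressure of 160 mm Hg or more and diastolic below 100 to restart sorafenib with no required hold and no fall in systolic pressure. The claim is that such a patient may restart, not that the protocol requires it.

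The conclusion rests on a literal reading of the restart cell and assumes that added drug treatment is indicated, so that the patient is grade 3 however the therapy clause is read. The documents give no rate of isolated systolic hypertension. The number affected among the 20 patients therefore cannot be derived, though it is probably small. The lower restart dose, added antihypertensives, checks every 2 days and the investigator's discretion all limit the consequence. The gap changes no endpoint, sample size or statistical figure.

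**What to change.** Amend the sorafenib cell of the grade 3 row in Section 5.1.2 to read: *Hold sorafenib until any symptoms have resolved, systolic BP is below 160 mm Hg and diastolic BP is below 100 mm Hg; then restart one dose level lower.* The value 160 is the systolic counterpart of the existing 100, since both are the lower bounds of grade 3. The clinical team may prefer a stricter systolic value. State the condition as pressure thresholds, not as a CTCAE grade. The grade definition counts the need for more than one drug, so a grade-based rule could keep out a patient whose pressure is well controlled on two.

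The edit is one table cell in a protocol amendment. For the patients concerned, the hold would last as long as systolic control takes, and some could pass 21 days and leave protocol therapy. Before surgery that matters somewhat: one patient is 1/20 = 5% of a trial whose primary endpoint is response to preoperative treatment. That cost is acceptable for a restart rule that matches its trigger.
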